A. Selection of participants: All consecutive patients of RA attending the OPD services of the department of Clinical Immunology will be included to reach a minimum sample size of in each group.

[figure not shown]
B. Patients will be assessed for eligibility and will be started on Methotrexate monotherapy initially and then only patients, who have moderate to severe disease activity inspite of 12 weeks of Methotrexate monotherapy, will be randomized to either of the 2 groups of DMARDs.

C. Allocation to groups:

Allocation concealment will be done by : Sequentially numbered, opaque, sealed envelopes (SNOSE) method

Group 1: MTX+LEF+HCQ

Group 2: MTX+SSZ+HCQ

F. Data Collection method including settings and periodicity: Patients aged above 18 years diagnosed as RA according to the 2010ACR-EULAR criteria will be screened and evaluated for inclusion in the study. The patients will be examined every 2 week interval during DMARD dose escalation & then every month for next 6 weeks of MTX and for 24 weeks for either groups.

a. Clinical evaluation:

- i. Adverse drug reactions (ADRs) – each visit
- ii. IHAQ, DAS28 - once at baseline and then at 12 weeks of MTX monotherapy and then at the end of 24 weeks treatment with either of Group 1 or group 2 drug.

b. Laboratory:

- i. Routine CBC/RFT/LFT: every 2 week interval during dose escalation & then every month for 12 weeks after starting the drug
- ii. ESR & hsCRP for disease activity evaluation: every month.
- iii. **USG** wrist, hand and feet (US-7 score)- at baseline and at 12 weeks of Group 1 or group 2 drug

G. List of variables and their measurement methods with standardization techniques:

a. (i) Independent variables

Socio-demographic profile:

- Age
- Gender

b. Outcome Variables:

Disease-related parameters –

Primary outcome measures:

- a. Disease activity (state) - DAS28

Secondary outcome measures:

- a. Functional ability – iHAQ
- b. Mean changes over time in:
 - i. Inflammatory parameters: ESR, hs-CRP
 - ii. Disease activity as per US-7 score
- c. Adverse drug reactions

Primary endpoint:

Proportion of patients in both groups achieving good response according to European League Against Rheumatism (EULAR) response criteria at the end of 12 weeks of combination therapy

Secondary endpoint:

1. Change in functional ability (Indian Health Assessment Questionnaire; iHAQ) at the end of 12 weeks of combination therapy
2. disease activity by US7 score at 12 weeks

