3. Safety of study medications (adverse drug reactions) during study period (till 24 weeks)
4. Proportion of patients achieving good EULAR response at the end of 24 weeks of combination therapy

Assessment of treatment response

The disease activity will be reassessed at the end of 12 and 24 weeks of random group allocation. The treatment response will be graded according to EULAR response criteria

Radiological assessment of disease activity

Musculoskeletal Ultrasound (**US-7 score**) will be performed in all patients in non blinded manner by the researcher

Clinical Evaluation :

- a. Demography: Age/Sex, ethnicity
- b. Detailed history and examination will be done for all patients
- c. Baseline evaluation of patient

Disease Activity: Indian Health associated questionnaire (IHAQ), Disease Activity Score-28 (DAS28)

Damage: Joint: Loss of motion, Deformity, Mal-alignment

- d. Extra-articular: Sicca symptoms & signs, sub cutaneous nodules, evidence of Interstitial Lung Disease (ILD), peripheral neuropathy, scleritis/episcleritis

Laboratory investigations

- i. **Routine:** Complete blood count (CBC), Erythrocyte Sedimentation Rate (ESR), Sugar (FBS/PP2BS), Liver Function Test (LFT), Renal function test (RFT), Mantoux Test, Viral markers (HIV, HBsAg, Anti HCV), urine analysis, Thyroid function test (TFT)

ii. **Ultrasound (USG)** wrist, hand and feet (US-7 score)

Immunological: High sensitivity C-reactive protein (hsCRP), Rheumatoid Factor (RF), Anti-CCP antibody (ACPA) in all participants .

After baseline evaluation, all consecutive patients with RA will be started on MTX monotherapy unless contraindicated. Patients not responding adequately to MTX monotherapy (DAS28 \geq 3.2) at the end of 12 weeks will be randomized to either of the 2 groups by block randomization after written informed consent.

- MTX+LEF+HCQ- Group 1
- MTX+SSZ+HCQ- Group 2

Concurrent treatment with the following drugs will be allowed during the study as per severity of symptoms and in cases of breakthrough pain:

1. Non-steroidal anti-inflammatory drugs (NSAIDs) - Tablet Diclofenac sodium 50mg twice a day (will be given for minimum duration) and if given on “as and when required” basis, patient will be asked to maintain an NSAID diary so as to know their requirement.

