2. Oral low dose Glucocorticoids (GC) - 7.5 mg/d for 4 weeks followed by 5 mg/day for 2 weeks followed by 5mg on alternate day for 2 weeks – as a bridge therapy. Thereafter, it can be given if disease flares (patient being symptomatic with continued DMARD therapy), with the maximum dose being 7.5mg/day.
3. Intra articular steroids-will be allowed during the study, as per severity of patient’s symptoms. The number of intraarticular injections required in each group will be calculated.

DMARD dosages used are:

For all patients as a standard protocol for management of all patients with RA :

1. **MTX** – starting dose 10 mg/week orally for 2 weeks → 15mg / week for 2 weeks 20 mg/ week for 2 weeks → 25mg/ week → assessment of response to MTX after 6 weeks (at the end of 12 weeks after starting MTX)
2. In patients , not tolerating adequate doses of oral MTX in the form of nausea, vomiting, the following strategies will be adopted- 1) dose will be split into two 2) oral MTX will be converted to im formulation.
3. T. Ondansetron 4mg twice a day for 2 days a week will be allowed in the study if patient has nausea or vomiting with MTX.
4. T. Folic acid 5 mg twice a week

Those not achieving adequate response to a maximum permissible dose of MTX (25 mg / week) ie. DAS28ESR >3.2 will be enrolled in the study after randomization:

For **Group 1**

1. T. MTX will be continued at 25mg/week
2. T. folic acid 5 mg twice per week
3. T. LEF -10 mg/day starting dose for 2 weeks → 20mg /day
4. T. HCQ 200 mg/day at night

For **Group 2**

1. T.MTX will be continued at 25mg/week
2. T. Folic acid 5 mg twice a week
3. T.SSZ 500mg once a day for 7 days → 500mg twice a day for 7 days →
500mg thrice a day for 7 days → 1gram twice a day
4. T. HCQ 200mg/day at night

Note: During the course of the study any patients developing extra-articular manifestations requiring different mode of therapy will be excluded from study (but intention to treat analysis will be used for analysis of results).

STATISTICAL ANALYSIS PLAN (SAP)

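### The protocol stops the routine blood, renal and liver panel after about 12 weeks, although the safety endpoint and the data collection form run to 24 weeks

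*Combined protocol and SAP*

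**What the plan says.** **Laboratory schedule.** Study Procedure, item F.b.i, is the only sentence that sets how often blood count, renal and liver tests are done on treatment: "every 2 week interval during dose escalation & then every month for 12 weeks after starting the drug". It does not name the drug. The next line, F.b.ii, has no stop date: "ESR & hsCRP for disease activity evaluation: every month".

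**Safety window.** Secondary endpoint 3 is "Safety of study medications (adverse drug reactions) during study period (till 24 weeks". Secondary endpoint 4 shows which clock the 24 weeks most plausibly follow: "Proportion of patients achieving good EULAR response at the end of 24 weeks of combination therapy". Section F has patients examined "every month for next 6 weeks of MTX and for 24 weeks for either groups", with adverse drug reactions recorded at each visit.

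**Form.** The follow-up investigations table in the Data Collection Proforma has columns at baseline and at 4, 8, 12, 16, 20 and 24 weeks. Its rows include haemoglobin, white cells, platelets, creatinine, bilirubin and AST/ALT. The table does not say what week 0 is.

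**Treatment.** Under DMARD dosages, patients in both groups continue methotrexate 25 mg/week. Leflunomide is stepped up after 2 weeks, and sulfasalazine reaches full dose after three 7-day steps.

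**The concern.** Comparing the safety of the two combinations is Objective 3. Exclusion criterion 3 lists leucopenia, thrombocytopenia, raised AST/ALT and low creatinine clearance as contraindications to DMARD therapy, so the plan itself treats these values as relevant to safety. A change in them need not cause symptoms. Asking about reactions at a visit will not reveal it if no sample is tested.

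The stated rule ends the panel well before the safety endpoint closes, while monthly blood for ESR and hsCRP continues. A team that follows the text and a team that fills in every cell of the form would monitor patients differently in the later weeks of methotrexate plus leflunomide or sulfasalazine.

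**Working it through.** **Inputs**
- Safety window: 24 weeks (Secondary endpoint 3), taken to run from randomisation.
- Panel: monthly for 12 weeks (F.b.i).
- Escalation: leflunomide 2 weeks; sulfasalazine 3 × 7 days = 3 weeks (DMARD dosages).
- Methotrexate run-in before randomisation: 12 weeks (Study Procedure E, item B).
- Last form column: 24 weeks.

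**Which drug F.b.i means.** Items F.a.ii ("at the end of 24 weeks treatment with either of Group 1 or group 2 drug") and F.b.iii ("at baseline and at 12 weeks of Group 1 or group 2 drug") name the group drug; F.b.i does not. The methotrexate dosing text has a similar phrase, "at the end of 12 weeks after starting MTX". The group drug is still the natural reading, because F.b.i describes monitoring around a dose escalation in a trial of the two combinations.

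**Uncovered weeks = 24 − last combination week covered**

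| Schedule followed | Covered to week | Uncovered weeks |
|---|---|---|
| F.b.i, 12 weeks from drug start | 12 | 24 − 12 = 12 (50%) |
| F.b.i, 12 weeks from end of escalation, leflunomide | 2 + 12 = 14 | 24 − 14 = 10 (42%) |
| F.b.i, 12 weeks from end of escalation, sulfasalazine | 3 + 12 = 15 | 24 − 15 = 9 (38%) |
| Form, week 0 = randomisation | 24 | 24 − 24 = 0 |

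**Panels not scheduled under F.b.i**
- Counted from drug start on a four-week grid: weeks 16, 20 and 24, so 3.
- Counted from drug start in calendar months: 24 weeks is about 5.5 months, so months 4 and 5, which is 2.
- Counted from the end of escalation in four-week steps: weeks 18 and 22 (leflunomide) or 19 and 23 (sulfasalazine), so 2.

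**Week 0 of the form**
- *For randomisation:* the DAS28, iHAQ and adverse-reaction rows end at 24 weeks. Response is to be assessed 12 and 24 weeks after allocation. The form opens with the enrolment date, and the dosing text places enrolment after randomisation.
- *For methotrexate start:* the protocol uses baseline for the evaluation before methotrexate. The steroid table has columns at baseline and months 4, 5 and 6. The US7 table has a 24-week column, although F.b.iii schedules no scan at 24 weeks of combination therapy.
- *Weighing:* with week 0 at methotrexate start, the 24-week column is combination week 24 − 12 = 12. The form then could not record Secondary endpoint 4 or the second half of Secondary endpoint 3. Randomisation is the better-supported origin.

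**The case against.** The strongest reply is that the form already settles the matter. On its better-supported reading it has a cell for every month to week 24, so F.b.i would be a wording slip and monitoring would be complete in practice. This stands as far as it goes: if the form governs, the gap is zero. But a column on a form is not an instruction that overrides the protocol sentence setting the frequency, and on this reading the two contradict each other.

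A figure in Study Procedure is not shown in the text available here and may display the time axis. The point therefore does not rest on week 0 being undefined everywhere in the plan. Whatever the figure shows, F.b.i still states 12 weeks.

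It is also fair that reactions are recorded at every visit, that the limit is the same in both arms, and that no separate laboratory endpoint is defined. These facts confine the concern to symptomless toxicity and give no ground for claiming bias. They do not reconcile a 12-week panel with a 24-week safety window.

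A reader might infer more in three ways, and the documents support none of them:
- **That no monthly panel is scheduled on combination therapy**, because the drug in F.b.i could be methotrexate. The wording allows this, but it is the less natural reading and leaves the form's later cells unexplained.
- **That the form itself stops at combination week 12.** This needs week 0 at methotrexate start, which would leave the form unable to record the 24-week endpoints.
- **That the safety comparison is biased, or that a number of events would be lost.** The documents give no laboratory reaction rate and no reason for the loss to differ between arms.

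**Conclusion.** The point holds as a conflict between F.b.i on one side and the safety endpoint and form on the other. It should be corrected, with medium confidence, because following a stated rule would leave later laboratory toxicity unscreened. The size depends on which document is followed: about 9 to 12 uncovered weeks under F.b.i, none under the form. These are alternatives, and the documents do not show which was used in practice.

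Three assumptions carry this: the drug in F.b.i is the group drug, the 24-week safety window runs from randomisation, and the form's week 0 is randomisation. The first two determine the 9 to 12 weeks; the third determines the zero. The primary endpoint at week 12 is unaffected.

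**What to change.** Reword F.b.i so that routine CBC, RFT and LFT are done every 2 weeks during leflunomide or sulfasalazine escalation and then every month until week 24 after randomisation, at the monthly visits and ESR/hsCRP draws already planned. Label week 0 of the form as randomisation, so that its 16-, 20- and 24-week cells are those panels.

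**Cost.** One protocol line and one label on the form, with no added visits. If the form was already followed from randomisation, no panels are added. Otherwise it is about 2 to 3 routine panels per patient: 140 × 2 = 280 to 140 × 3 = 420 in all. If the planned 20% dropout has occurred by week 12, 140 × 0.8 = 112 patients remain, which gives 112 × 2 = 224 to 112 × 3 = 336.

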| | Baseline | 4mo | 5mo | 6mo |
|---------------|-----------------|------------|------------|------------|
| IA Steroids | | | | |
| Oral steroids | | | | |

| | Baseline | 4 week | 8 week | 12 week | 16 week | 20 week | 24 week |
|--------------------------|-----------------|---------------|---------------|----------------|----------------|----------------|----------------|
| TJ28 | | | | | | | |
| SJ28 | | | | | | | |
| VAS | | | | | | | |
| ESR | | | | | | | |
| hsCRP | | | | | | | |
| DAS28 | | | | | | | |
| iHAQ | | | | | | | |
| Morning stiffness | | | | | | | |

| | | | | | | | |
|--------------------------------|--|--|--|--|--|--|--|
| Extraarticular features | | | | | | | |
| Adverse drug reactions | | | | | | | |

FOLLOW UP INVESTIGATIONS

| Investigations | Baseline | 4W | 8W | 12W | 16W | 20W | 24W |
|-----------------------|-----------------|-----------|-----------|------------|------------|------------|------------|
| Hb | | | | | | | |
| TLC | | | | | | | |
| DLC | | | | | | | |
| MCV | | | | | | | |
| Platelets | | | | | | | |
| Peripheral smear | | | | | | | |
| Urine albumin | | | | | | | |
| Microscopy | | | | | | | |
| Blood urea | | | | | | | |
| Sr. Creatinine | | | | | | | |
| Bilirubin (T/D) | | | | | | | |
| AST/ ALT | | | | | | | |
| ALP/GGT | | | | | | | |
| Total protein /Alb | | | | | | | |
| CPK / LDH | | | | | | | |
| Sugar (AC/PC) | | | | | | | |
| CH/TG/HDL/LDL | | | | | | | |
| CT/USG/MRI | | | | | | | |
| ECG/ECHO | | | | | | | |

| US7 Score | | Baseline | 12 week | 24 week |
|------------------|-----------|-----------------|----------------|----------------|
| Synovitis | GS | | | |
| | PD | | | |
| TS | GS | | | |
| | PD | | | |
| Erosion | GS | | | |

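### The US-7 schedule text puts the reference scan before methotrexate and lists none at randomisation, so US-7 change would include the methotrexate run-in; the data form does not settle the timing

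*Combined protocol and SAP*

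**What the plan says.** Section F of the protocol (data collection), item b.iii, schedules ultrasound "wrist, hand and feet (US-7 score)- at baseline and at 12 weeks of Group 1 or group 2 drug". That is two scans.

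Item a.ii of the same section schedules DAS28 and iHAQ "once at baseline and then at 12 weeks of MTX monotherapy and then at the end of 24 weeks treatment". There, baseline and the end of MTX monotherapy are separate time points.

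The clinical evaluation section lists the US-7 ultrasound among the laboratory investigations and continues: "After baseline evaluation, all consecutive patients with RA will be started on MTX monotherapy unless contraindicated". Patients with an inadequate response "at the end of 12 weeks will be randomized to either of the 2 groups by block randomization after written informed consent".

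US-7 appears twice among the outcomes. Under the secondary outcome measures, "Disease activity as per US-7 score" is an item under the heading for average change over time. Secondary endpoint 2 is worded as a level: "disease activity by US7 score at 12 weeks".

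The data collection proforma heads its ultrasound table "US7 Score | | Baseline | 12 week | 24 week" and does not say from when the weeks are counted.

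**The concern.** Objectives 1 and 2 ask how each combination performs in patients who have already failed MTX. The natural reference for that question is the state at randomisation. If the only earlier scan is taken before MTX, the change to week 12 of combination therapy adds the effect of 12 weeks of MTX to that of the combination, and the two parts cannot be separated afterwards. Nobody could check whether the groups had similar ultrasound scores when they were allocated, or adjust for a difference. A scan missed at that visit cannot be recovered later.

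**Working it through.** **1. The schedule text side by side**

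| Visit | DAS28, iHAQ (F.a.ii) | US-7 (F.b.iii) |
|---|---|---|
| Baseline, before MTX | yes | yes |
| End of 12 weeks of MTX (randomisation) | yes | not listed |
| Week 12 of combination | not listed here | yes |
| Week 24 of combination | yes | not listed |

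The interval between the US-7 scans is 12 + 12 = 24 weeks, half of it before randomisation.

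**2. The form under each possible clock**

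- Weeks counted from MTX start: the 12-week column is the randomisation visit and the 24-week column is week 12 of combination. A randomisation scan exists.
- Weeks counted from randomisation: the baseline column is the randomisation scan. A randomisation scan exists.
- Mixed (baseline before MTX, then weeks 12 and 24 of combination): no randomisation scan.

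None of the three gives the two scans of F.b.iii. The form's steroid table, headed "Baseline | 4mo | 5mo | 6mo", leans to the first clock. The secondary endpoint at 24 weeks of combination, with disease-activity columns that stop at 24 weeks, leans to the second.

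**3. Effect on the estimates**

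Write Y0, Y1 and Y2 for US-7 before MTX, at randomisation and at week 12 of combination. Then

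Y2 − Y0 = (Y1 − Y0) + (Y2 − Y1).

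Within an arm, the mean of Y2 − Y0 is off by the whole run-in change. Between arms, Y1 − Y0 arises before allocation, has the same expectation in both groups, and cancels.

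Illustration in SD units. Every value is assumed, because the documents give no US-7 mean, SD or correlation: run-in change −0.5; combination change −0.6 in Group 2; true arm difference −0.30; correlations 0.6 (Y0,Y1), 0.6 (Y1,Y2) and 0.4 (Y0,Y2). The results come from 20,000 simulated trials with 70 per group.

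| Analysis | Arm difference | SE | Group 2 within-arm change |
|---|---|---|---|
| Change from pre-MTX scan | −0.300 | 0.187 | −0.5 − 0.6 = −1.1 |
| Change from randomisation scan | −0.300 | 0.152 | −0.6 |
| Week-12 score alone | −0.298 | 0.169 | none |

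The 70 per group is the plan's own figure, set for EULAR response and not for US-7. It reproduces with a one-sided 5% level: 2 × 0.75 × 0.25 × (1.645 + 0.842)² / 0.20² = 57.96, so 58, and 58 × 1.2 = 69.6, so 70.

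**4. Precision over a range**

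With equal SDs and correlation r between the reference scan and the week-12 score, the variance of the arm difference is proportional to 2(1 − r) for change scores and to 1 − r² for a baseline-adjusted analysis. The table gives variance with the pre-MTX scan divided by variance with a randomisation scan. The randomisation scan is assumed to correlate 0.2 more strongly, being nearer in time.

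| r pre-MTX | r randomisation | Change score | Adjusted |
|---|---|---|---|
| 0.2 | 0.4 | 0.8/0.6 = 1.33 | 0.96/0.84 = 1.14 |
| 0.4 | 0.6 | 0.6/0.4 = 1.50 | 0.84/0.64 = 1.31 |
| 0.6 | 0.8 | 0.4/0.2 = 2.00 | 0.64/0.36 = 1.78 |

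If the two correlations were equal, both ratios would be 1. When r is below 0.5, 2(1 − r) exceeds 1, so change from that scan is less precise than the week-12 score alone.

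**5. Unseen imbalance**

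The SE of the chance difference in US-7 at randomisation is SD × √(2/70) = 0.169 SD. The 95% range is ±1.96 × 0.169 = ±0.33 SD.

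**The case against.** Much of the case on the other side stands.

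- **The form may already provide the scan.** Both internally consistent clocks include one at randomisation. A reader of F.b.iii alone might infer that US-7 is never measured there. The documents do not support that, and the flow figure, which might bear on it, is not shown. The form does not rescue the plan either: it has three columns against two scheduled scans and no time origin, so a site may follow either.
- **Section F is not a complete schedule.** Item a.ii omits DAS28 at week 12 of combination, although the primary endpoint needs it. But the section on assessing treatment response supplies that reading, and no comparable text supplies a US-7 scan at the end of MTX.
- **The randomised comparison is sound.** A reader might infer that the MTX effect contaminates it. It does not: the run-in change cancels in expectation, and secondary endpoint 2 is a week-12 score that needs no baseline. Chance imbalance of the size in step 5 is already covered by the standard error of a randomised comparison.
- **The within-arm harm is conditional.** Objectives 1 and 2 do not name US-7, and the SAP specifies only unadjusted between-group tests for continuous data. The route to harm is the secondary outcome of average change over time, or a within-arm statement built on it. The adjusted-analysis ratios matter only if such an analysis is added.
- **Consent.** A reader might also infer that research scans precede consent. That cannot be judged here: the consent pages are not in the material, and the protocol describes the MTX phase as standard management.

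**Conclusion.** The point holds as a gap in the schedule text plus a mismatch with the form, on a secondary outcome. If F.b.iii is followed, US-7 change includes 12 weeks of MTX monotherapy in its 24, within-arm change cannot be attributed to the combination, and US-7 balance at randomisation cannot be checked or adjusted for.

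The within-arm error equals the run-in change, whatever that is. The −0.5 SD used above is a placeholder, and the change could be smaller because only patients with persisting disease activity are randomised.

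The between-arm comparison loses precision only: about 1.3 to 2.0 times the variance for change scores and 1.1 to 1.8 times for an adjusted analysis. Those ranges rest on equal SDs, on the assumed correlations, and on the randomisation scan being the better predictor by 0.2. The absence of bias refers to patients who have their week-12 scan; handling of missing scans is a separate question. The primary endpoint and the sample size are unaffected.

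**What to change.** 1. In section F.b.iii and in the baseline work-up list, schedule the reference US-7 scan at the randomisation visit: end of 12 weeks of MTX, after consent, before the first combination dose.
2. Define US-7 change as that scan to week 12 of combination therapy. If the week-12 score is adjusted, use that scan as the covariate and say so in the SAP.
3. State the time origin of the form's US-7 columns, and reconcile the 24-week column with F.b.iii by either scheduling that scan or removing the column.

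The cost is wording in the protocol, SAP and form. Under F.b.iii the number of scans per randomised patient stays at two, and patients who respond to MTX no longer need one. The pre-MTX US-7 value is lost, but no stated endpoint uses it. If the sponsor already intended a scan at randomisation, this only clarifies the text.

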The trial is designed as a non-inferiority pragmatic trial. The assessment will be done in unblinded fashion by the researcher. Arbitrarily considering EULAR good response rate (primary endpoint) of 75% with SSZ based triple regimen (tREACH and TICORA study) and non-inferiority margin of $\Delta = (-20\%)$ for LEF, a sample size of 140 (70 in each group) was determined using nMaster sample size calculator (version 2 software) using 2-sided confidence levels (CI) of 95%, power of 80% and dropout rate of 20%.

Data will be analyzed using SPSS (IBM pasw statistics, version 19.0) for windows. For quantitative data [DAS28ESR, iHAQ], normality of distribution will be checked by Shapiro-Wilks W test. Continuous data was presented as median and interquartile range (IQR₂₅₋₇₅) / mean with SD as appropriate. Mann-Whitney U test / Students t test will be used for comparison between median/ mean of 2 groups respectively. Qualitative or categorical variables (such as EULAR good response) will be described as proportions and will be tested using Chi-square. Odds ratio (OR) – odds of achieving the outcome (treatment response) in patients exposed to LEF in comparison to patients not exposed to LEF (SSZ group) along with 95% confidence interval and p-value will be used to study the statistically significant difference in treatment outcome between 2 groups. P-value of <0.05 was considered as significant.

The primary endpoint will be analyzed by both intention-to-treat (ITT) and per-protocol (PP) analysis. The rest of the parameters will be analyzed by ITT analysis only. Patients who do not complete the study, the last observation will be taken as their outcome for ITT analysis. For missing data, the last available readings will be carried forward in case of patients who are not available for the endpoint assessment. Non-inferiority testing will be done by using a 95% confidence interval (CI) of the difference between the proportions of patients achieving the primary endpoint between 2 groups. Extension of CONSORT 2010 statement will be used for reporting of non-inferiority of the LEF group.

DATA COLLECTION PROFORMA

CODE NO:

Date of enrollment:

Name/ age/ sex/ CCR no :

Contact number

Disease duration:

Co-morbid conditions (with duration):

Personal history (habits/addictions):

Treatment history:

Family history:

Baseline Investigations:

RF:

HIV:

HBsAg:

HCV:

Anti-CCP:

Mantoux test:

Drug

Dose

since when

Side effects

1

2

3

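### The only safety endpoint is adverse drug reactions, judged unblinded with no causality rule, and safety recording after removal from the study is not provided for, so the LEF–SSZ safety comparison is open to bias of unknown direction

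*Combined protocol and SAP*

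**What the plan says.** Objective 3 is to compare the two regimens on safety as well as efficacy, and the research question names both. Safety then appears as one item, secondary endpoint 3: "Safety of study medications (adverse drug reactions) during study period (till 24 weeks"). Section F (Data Collection method) sets the collection rule: "Adverse drug reactions (ADRs) – each visit". The documents do not define an adverse drug reaction, plan to record all adverse events, or give a causality method, severity grading or independent review.

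The first paragraph of the SAP states: "The assessment will be done in unblinded fashion by the researcher". This is a general statement that exempts no outcome.

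The note after the DMARD dosages says that "any patients developing extra-articular manifestations requiring different mode of therapy will be excluded from study", and the same sentence continues in parentheses: "but intention to treat analysis will be used for analysis of results". For the secondary endpoints the SAP adds: "The rest of the parameters will be analyzed by ITT analysis only". For non-completers: "Patients who do not complete the study, the last observation will be taken as their outcome for ITT analysis".

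The follow-up table in the data collection proforma runs from baseline to week 24 and has separate rows for extra-articular features and for adverse drug reactions. The baseline clinical evaluation lists interstitial lung disease and peripheral neuropathy among the extra-articular findings.

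**The concern.** An endpoint made up of drug reactions contains a causal judgement. MTX and HCQ are common to both arms, so the person completing the form has to decide whether an event is due to a drug at all while knowing whether the patient takes LEF or SSZ. Without a written rule, nothing keeps that decision the same in both arms. A difference in reaction rates could then come from attribution, and a true difference could be hidden by it.

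Two further gaps affect the same count. A patient removed under the note may have later reactions that nobody is instructed to record. And a new event on treatment, such as lung disease or neuropathy, may be entered only in the extra-articular row, with nothing to say that this row enters the safety comparison. Patients with extra-articular features such as interstitial lung disease are excluded at entry, so an event of that kind after randomisation would be new, and whether disease or drug caused it is the very judgement left undefined.

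At stake is the safety half of the research question. The primary efficacy endpoint is not affected.

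**Working it through.** The documents give no figure for the safety endpoint, so there is none to reproduce. The size of the problem can be shown only under assumptions.

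**Inputs from the documents.** 70 patients per arm (sample size section and SAP, including the 20% dropout allowance); chi-square test for categorical variables and significance at p < 0.05 (SAP).

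**Assumed inputs.** True risk r of any adverse event, equal in both arms: 30%, 40% or 50%. Share of events attributed to the drug: 80% in one arm (a₁); 80%, 70% or 60% in the other (a₂). Which arm has the higher share is arbitrary.

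**Step 1: attribution.** Reaction rates are p₁ = r × a₁ and p₂ = r × a₂, and the spurious gap is d = p₁ − p₂. With p̄ = (p₁ + p₂)/2, the standard error under no difference is SE₀ = √(2p̄(1 − p̄)/70), and the actual one is SE = √(p₁(1 − p₁)/70 + p₂(1 − p₂)/70). By normal approximation, the chance of a significant result is 1 − Φ((1.96·SE₀ − d)/SE) + Φ((−1.96·SE₀ − d)/SE).

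Example, r = 40% and 80% v 60%: p₁ = 0.32, p₂ = 0.24, d = 0.08, p̄ = 0.28. SE₀ = √(2 × 0.28 × 0.72/70) = 0.0759 and SE = √((0.2176 + 0.1824)/70) = 0.0756. Then (1.96 × 0.0759 − 0.08)/0.0756 ≈ 0.91, which gives an upper tail of about 0.182. The lower tail adds about 0.001, for a total of 18.3%.

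| True risk | Attribution | Reaction rates | Gap (points) | False-positive rate |
|---|---|---|---|---|
| 30% | 80% v 70% | 24% v 21% | 3 | 7.1% |
| 40% | 80% v 70% | 32% v 28% | 4 | 8.1% |
| 50% | 80% v 70% | 40% v 35% | 5 | 9.3% |
| 30% | 80% v 60% | 24% v 18% | 6 | 14.0% |
| 40% | 80% v 60% | 32% v 24% | 8 | 18.3% |
| 50% | 80% v 60% | 40% v 30% | 10 | 23.5% |

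With equal attribution (80% v 80%) the gap is 0 and the rate is 5%.

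**Step 2: removal.** Suppose k more patients are removed in one arm and half of their reaction risk r goes unobserved. That arm's proportion falls by (k/70) × r × ½.
- k = 1, r = 30%: (1/70) × 0.30 × 0.5 = 0.0021, or 0.2 points.
- k = 7, r = 50%: (7/70) × 0.50 × 0.5 = 0.025, or 2.5 points.

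Attribution is therefore the larger risk. Removal matters only if removals are many and unequal.

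**Step 3: passages side by side.** ITT keeps a removed patient in the denominator. Carrying the last observation forward fixes that patient's safety status at the last recorded visit, so a reaction after that visit counts as no reaction. Keeping the patient in the analysis does not supply the missing observation.

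**Step 4: laboratory data as a safeguard.** Section F schedules blood count, renal and liver tests through 12 weeks after starting the drug. The safety endpoint runs to week 24, and the proforma has laboratory columns to week 24. These passages do not agree, and no laboratory event is defined as an outcome.

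**The case against.** The strongest reply is that attribution is inferred from one term. The documents describe no attribution step and name no judge of causality, and the sentence on unblinded assessment is general. The proforma also records blood counts, creatinine, liver enzymes and extra-articular features whatever their suspected cause. In an openly pragmatic, unblinded trial some of this is accepted by design. Modest differential attribution raises the false-positive rate only to 7–9%, and even an 8-point spurious gap would be non-significant more than four times in five.

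Part of this stands. The inference rests on the ordinary meaning of a drug reaction, and the size rests on assumptions. But a pragmatic design explains the lack of blinding, not the lack of an event definition. And recording data on a form does not make them part of the endpoint.

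A reader might infer more than the documents support:
- *That any new extra-articular feature removes the patient and the data.* The note applies only where a different mode of therapy is required, and it keeps these patients in ITT.
- *That no safety data are collected after removal.* The plan is silent; it does not say that recording stops.
- *That LEF patients are seen less often than SSZ patients.* SSZ escalation takes 7 + 7 + 7 = 21 days and LEF escalation 2 weeks, so week 2 is the only two-weekly visit within escalation in either arm; monthly visits then fall at weeks 6 and 10 in both. Even if week 4 is counted for SSZ (2, 4, 8, 12), adding the required week-12 assessment gives LEF four visits too (2, 6, 10, 12).
- *That the bias favours one drug.* The research hypothesis is worded as LEF being inferior, but in a non-inferiority trial this may simply state the null. It does not settle the direction.

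**Conclusion.** The concern holds in limited form. The safety comparison is a stated objective that rests on an undefined, attribution-dependent endpoint assessed without blinding, so it can be biased in either direction. With equal true risks of 30–50% and 70 per arm, the spurious gap is 3–5 points under 80% v 70% attribution and 6–10 points under 80% v 60%. The false-positive rate is 7–9% and 14–24% respectively, against 5% with equal attribution. The gap in recording after removal is real but smaller, about 0.2–2.5 points if 1 to 7 extra patients are removed in one arm and half of their risk is unobserved. The attribution shares, event risks and removal counts are assumptions; the documents give none of them. The analysis does not show that bias will occur, only that the plan has no protection against it. The change is worth making because it is cheap and the comparison is one the trial sets out to report.

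**What to change.** - Redefine secondary endpoint 3 as all adverse events with onset from randomisation to week 24, whatever the suspected cause, compared by randomised arm. Show drug attribution descriptively beside it.
- State that new extra-articular events after randomisation count in that endpoint, whichever row of the proforma they are entered in.
- In the note after the DMARD dosages, replace exclusion from the study with continued outcome and safety recording to week 24. This concerns data collection only and leaves the clinical management of these patients unchanged.
- Reconcile the laboratory schedule and visit wording in section F with the proforma's common calendar to week 24.

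The eligibility cut-offs for liver enzymes, leucocytes and platelets should not be reused as safety-event thresholds on the strength of this point; the plan does not offer them for that purpose.

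The cost is the wording of one endpoint and one note, a clarification to the form, and slightly more event recording. Headline event rates will be higher in both arms. Whether more laboratory testing follows depends on how the 12-week text and the 24-week form are reconciled.
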